8.2. Setting

All patients receiving BESPONSA will be included in this investigation.

PFIZER CONFIDENTIAL

CT24-WI-JPN-GPSP01-RF09 8.0 Non-Interventional Study Protocol Template for Secondary Data Collection

Study 01-Nov-2023

Page 13 of 33

Inotuzumab

B1931024 NON-INTERVENTIONAL STUDY PROTOCOL

Amended 8, 12 December 2023

[INDICATION]

Relapsed or refractory CD22-positive ALL

[DOSAGE AND ADMINISTRATION]

The usual dosage for adults is 0.8 mg/m² (body surface area) of inotuzumab ozogamicin (genetical recombination) on Day 1 and 0.5 mg/m² (body surface area) on Days 8 and 15 once daily by intravenous infusion over at least 1 hour followed by a treatment-free interval. The length of cycle is 21 to 28 days for Cycle 1 and 28 days for Cycles 2 and subsequent cycles. The treatment should be repeated. The number of cycles should be decided while taking account of the schedule of HSCT. The dose should be decreased as necessary according to the patient's condition.

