## 2.1. Study Design

- **Target population**

*All patients who received this drug will be included in this survey.*

- **Survey period**

*The scheduled periods of this survey are as follows:*

*Survey period: From the date of launch of this drug to 5 years\**

*Registration period: From the date of launch of this drug to the time of lifting of approval conditions for all-case survey\**

*\*: Patients who started to receive this drug on or after May 1, 2020 will only be registered.*

The protocol may be changed to terminate the registration only period, but this change will not affect the SAP.

- **Observation period**

*Observation period: The observation period is to be 52 weeks for patients who did not undergo hematopoietic stem cell transplant (HSCT) within 52 weeks after the start of the treatment with this drug and up to 52 weeks after HSCT for patients who underwent HSCT within 52 weeks after the start of this drug. If patients who started to receive this drug on or before April 30, 2020 are transferred to another hospital during the observation period, the transferred hospitals will be requested to conclude a contract for the conduct of this survey, and the information at the transferred hospitals will be collected as much as possible.*

*[1] Treatment Period*

*From the start of treatment to Day 28 post-final dose: For assessments of safety (e.g., adverse events) and effectiveness (hematologic response, survival time)*

*[2] Follow-up period*

*For 52 weeks from 29 days after the final dose (for patients who did not undergo HSCT by 52 weeks after the start of treatment) or for 52 weeks after HSCT (for patients who underwent HSCT by 52 weeks after the start of treatment): For assessments of safety (VOD/SOS) and effectiveness (survival time)*

The starting point for the 52 week follow-up after HSCT is the day of the last HSCT performed within 52 weeks after the start of this drug.

- **Safety specification**

See Protocol Section 7.1.

- **Sample size and its rationale**

*Of the patients who have received this drug, a total of 176 patients with relapsed or refractory CD22 positive (CD22+) acute lymphocytic leukemia (ALL) will be included in the safety analysis set. In consideration of dropouts during the survey, 200 patients will be registered.*

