- Peripheral blast count before conditioning for the first HSCT after the start of this drug [≤ 1000 /µL, > 1000 /µL, not performed]
- Myeloblast count before conditioning for the first HSCT after the start of this drug [≤ 50%, > 50%, not performed]
- Time from the date of final dose of this drug to the date of the first HSCT after the start of this drug [< 4 weeks, ≥ 4 weeks to < 8 weeks, ≥ 8 weeks to < 12 weeks, ≥ 12 weeks to < 16 weeks, ≥ 16 weeks]
- Treatment cycles [1 cycle, 2 cycles, 3 cycles, 4 cycles, 5 cycles, 6 cycles, > 6 cycles]
- Treatment cycles [≤ 3 cycles, ≥ 4 cycles]
- Dosing of > 1.8 mg/m^2 per cycle [absent, present] (Considered to be present, if there is a cycle of > 1.8 mg/m^2 per cycle during the treatment period.)
- Pregnancy [absent, present] \* Pregnancy during the treatment period. Limited to cases in which information on pregnancy is collected
- Best overall response [complete remission (CR) or complete remission with incomplete hematologic recovery (CRI), progression or relapse, indeterminate/other, not performed]
- Minimal residual disease (MRD) [negativity achieved, negativity not achieved, test not performed]
  - \* Irrespective of the result of best overall response.
- Best overall response and MRD [CR/CRI achieved and negativity achieved, CR/CRI achieved and negativity not achieved, progression/relapse and negativity achieved, progression/relapse and negativity not achieved] \* "Indeterminate/other" and "not performed" are excluded.
- Adverse drug reactions that occurred during the treatment period - liver disorder as a safety specification [absent, present]

Subgroup analyses of hematologic response and MRD will be performed for the following patient characteristics and other factors:

- Age [< 15 years, ≥ 15 to < 65 years, ≥ 65 years]
- Age [< 18 years, ≥ 18 to < 55 years, ≥ 55 years]
- Age [< 15 years, ≥ 15 to < 40 years, ≥ 40 years]
- Disease name [Relapsed CD22+ acute lymphocytic leukemia (ALL), refractory CD22+ ALL]
- Chromosome karyotype [normal, t (4;11), unknown]
- Chromosome karyotype [Philadelphia chromosome positive, negative, unknown]\* Philadelphia chromosome is considered positive if the chromosome karyotype is t(9;22).
- Hemoglobin level immediately before the start of this drug [< 10 g/dL, ≥ 10 g/dL, not performed]
- Platelet count immediately before the start of this drug [< 10 × 10^4/µL, ≥ 10 × 10^4/µL, not performed]

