#### 8.1.3. Binary variables

For binary variables, patients falling into each binary category will be summarized in terms of frequency (n) and proportion. If a confidence interval (CI) is determined for a proportion, the two-sided 95% CI will be determined using the exact method.

For a comparison of proportion between subgroups, the risk ratio (RR) and its 95% CI will be determined. In addition, the RRs and their 95% CIs will be graphically presented.

For statistical tests, Fisher's exact test will be performed to test correlations in nominal scale data, and Cochran-Armitage test (exact method) to test correlations in ordinal scale data. If, however, it is difficult to use the exact method, chi-square test or Cochran-Armitage test with normal approximation will be used as an alternative to the exact method.

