### **8.2.3. Safety analyses**

Adverse drug reactions (ADRs) and adverse events (AEs) that occurred in the following periods will be collected for summary: for ADRs and AEs other than VOD/SOS, those that occurred from the start of this drug to 28 days after the final dose of this drug will be collected; for ADRs and AEs of VOD/SOS in patients who did not undergo HSCT within 52 weeks after the start of this drug, those that occurred within 52 weeks after the start of this drug will be collected; for ADRs and AEs of VOD/SOS in patients who underwent HSCT within 52 weeks after the start of this drug, those that occurred within 52 weeks after the last HSCT will be collected. The listings will include all events reported in this survey.

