#### **8.2.3.1. Adverse drug reactions**

- **All adverse drug reactions**

The number and proportion of patients with adverse drug reactions will be tabulated by SOC and PT.

- **Details of adverse drug reactions**

ADRs categorized by each of the following factors will be summarized in terms of number and proportion of patients with ADRs by SOC and PT:

- Seriousness [serious, non-serious]
- Known/Unknown [known, unknown]
- Action taken (additional treatment for the AE) [performed, not performed]
- Action taken [discontinuation of treatment, temporary suspension or dose reduction, none]
- Outcome [fatal, not recovered, recovered with sequelae, recovering, resolved/recovered, unknown]
- CTCAE Grade (1) [1, 2, 3, 4, 5, unknown]
- CTCAE Grade (2) [ $< 3$ ,  $\geq 3$ , unknown]

Multiple occurrences of the same adverse drug reaction (with the same PT) in the same patient will be handled as follows in the summary:

- Seriousness: If both serious and non-serious events of the same AR occurred in the same patient, the patient will be counted as one with a serious reaction.
- Known/Unknown: If both known and unknown events of the same AR occurred, the patient will be counted as one with an unexpected reaction.
- Action taken: If multiple types of actions were taken for the same AR in the same patient, one action will be adopted in the order of priority of "discontinuation of treatment", "temporary suspension or dose reduction", and "none".
- Outcome: See below
- CTCAE Grade: If there are multiple grades, the highest grade will be used.

In the summary by outcome, multiple events of the same AR in the same patient will be handled as follows:

- Outcome: If multiple different outcomes were reported, one category of outcome will be adopted from "fatal", "not recovered", "unknown", "recovered with sequelae", "recovering", and "resolved/recovered" with priority in this order.

Each SOC and PT of serious ADRs will be summarized by outcome.

- **Safety specification**

Patients who experienced the events identified as the safety specification will be summarized in terms of n and proportion. Similar summary will also be performed by CTCAE Grade [ $< 3$ ,  $\geq 3$ , unknown].

In addition, events identified as the safety specification will be summarized in terms of number and proportion of patients with such events for each SOC and PT by actions taken and outcome thereof.

- **Timing of onset of adverse drug reactions**

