#### 8.2.3.4. Subgroup analyses

Patients who experienced at least one AR will be summarized in terms of n and proportion by each of the following factors selected from those specified in Section 5.4. To investigate the correlation between patient characteristics and occurrence of ADRs, statistical tests specified in Section 8.1.3 and risk ratio estimation will be performed.

- Age [ $< 15$  years,  $\geq 15$  to  $< 65$  years,  $\geq 65$  years]
- Age [ $< 18$  years,  $\geq 18$  to  $< 55$  years,  $\geq 55$  years]
- Age [ $< 15$  years,  $\geq 15$  years to  $< 40$  years,  $\geq 40$  years]
- Disease name
- Chromosome karyotype
- Chromosome karyotype \* Philadelphia chromosome is considered positive if the chromosome karyotype is t(9;22).
- Hepatic impairment
- Renal impairment
- Medical history (past) - VOD/SOS
- Medical history (past) - GVHD
- Medical history (past) - Hepatitis or hepatic disease
- Medical history (present) - VOD/SOS
- Medical history (present) - GVHD
- Medical history (present) - Hepatitis or hepatic disease

- ECOG PS before the start of this drug
- AST and ALT levels immediately before the start of this drug
- $\gamma$ -GTP level immediately before the start of this drug
- Total bilirubin level immediately before the start of this drug
- Hemoglobin level immediately before the start of this drug
- Platelet count immediately before the start of this drug
- Peripheral blast count immediately before the start of this drug
- Myeloblast count immediately before the start of this drug
- Salvage line of the induction treatment with this drug
- HSCT before the start of this drug
- Pregnancy \* Pregnancy during the treatment period. Limited to cases in which information on pregnancy is collected

Furthermore, patients who experienced ADRs will be summarized in terms of n and proportion for each SOC and PT by each of the following factors selected from those specified in Section 5.4. In addition, risk ratios for the proportion of patients with ADRs for different subgroups will be determined as per Section 8.1.3 and presented graphically. If, however, there is a category with less than 10 patients and after reconsideration it is considered difficult to determine the risk ratio for the category, it will not be determined for the relevant category. To investigate the correlation between patient characteristics and occurrence of ADRs, statistical tests specified in Section 8.1.3 will be performed.

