- Age [< 15 years,  $\geq 15$  to  $< 65$  years,  $\geq 65$  years]
- Age [< 18 years,  $\geq 18$  to  $< 55$  years,  $\geq 55$  years]
- Age [< 15 years,  $\geq 15$  to  $< 40$  years,  $\geq 40$  years]
- Hepatic impairment
- Renal impairment
- HSCT before the start of this drug
- Total dose per cycle  $> 1.8$  mg/m^2
- Pregnancy \* Pregnancy during the treatment period. Limited to cases in which information on pregnancy is collected

Similarly, ADRs meeting definition of liver disorder including safety specification events of VOD/SOS will be analyzed by each of the following factors. Similar analyses will also be performed for ADRs of Grade 3 or higher based on CTCAE v4.0.

- Age [< 15 years,  $\geq 15$  to  $< 65$  years,  $\geq 65$  years]
- Age [< 18 years,  $\geq 18$  to  $< 55$  years,  $\geq 55$  years]
- Age [< 15 years,  $\geq 15$  to  $< 40$  years,  $\geq 40$  years]
- Hepatic impairment
- Medical history (past) - VOD/SOS
- Medical history (past) - Hepatitis or hepatic disease
- Medical history (present) - VOD/SOS
- Medical history (present) - Hepatitis or hepatic disease
- ECOG PS before the start of this drug

- AST and ALT levels immediately before the start of this drug
- $\gamma$ -GTP level immediately before the start of this drug
- Total bilirubin level immediately before the start of this drug
- Platelet count immediately before the start of this drug
- Peripheral blast count immediately before the start of this drug
- Salvage line of the induction treatment with this drug
- HSCT before the start of this drug

Similarly, ADRs meeting definition of safety specification events of myelosuppression will be analyzed by each of the following factors. Similar analyses will also be performed for ADRs of Grade 3 or higher based on CTCAE v4.0.

- Age [ $< 15$  years,  $\geq 15$  to  $< 65$  years,  $\geq 65$  years]
- Age [ $< 18$  years,  $\geq 18$  to  $< 55$  years,  $\geq 55$  years]
- Age [ $< 15$  years,  $\geq 15$  to  $< 40$  years,  $\geq 40$  years]
- Hepatic impairment
- Renal impairment
- Total dose per cycle  $> 1.8 \text{ mg/m}^2$
- ECOG PS before the start of this drug
- White blood cell count immediately before the start of this drug
- Neutrophil count immediately before the start of this drug
- Platelet count immediately before the start of this drug
- Salvage line of the induction treatment with this drug
- HSCT before the start of this drug

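### The '> 1.8 mg/m² per cycle' factor can be set by doses given after the reaction, so its ADR risk ratio can be biased in either direction even if dose has no effect

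*SAP*

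**What the plan says.** SAP 5.4 lists dosing above 1.8 mg/m² per cycle as an absent/present factor and explains it as follows: "Considered to be present, if there is a cycle of" more than 1.8 mg/m² at any point in the treatment period. SAP 2.1 defines that period: "From the start of treatment to Day 28 post-final dose". SAP 8.2.3 uses the same window for ADRs other than VOD/SOS: "those that occurred from the start of this drug to 28 days after the final dose of this drug will be collected".

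SAP 8.2.3.4 applies the factor, there called "Total dose per cycle" above 1.8 mg/m², to ADRs by SOC and PT and to myelosuppression, infection and hemorrhage, each of these three also at Grade 3 or higher. The estimate is crude: "risk ratios for the proportion of patients with ADRs for different subgroups will be determined as per Section 8.1.3 and presented graphically". SAP 8.1.3 gives the method: "For a comparison of proportion between subgroups, the risk ratio (RR) and its 95% CI will be determined". It has no time axis.

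Both documents expect dosing to respond to how the patient is doing. Protocol 8.2 states: "The dose should be decreased as necessary according to the patient's condition". SAP 8.2.3.1 summarizes ADRs by action taken, with the categories "discontinuation of treatment, temporary suspension or dose reduction, none".

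For this factor the SAP has no landmark, no restriction to cycles before onset, no time-dependent covariate, no adjustment for number of cycles and no caution.

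**The concern.** Exposure is read from the whole treatment course, while the outcome may occur in Cycle 1. This opens two routes to bias.

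- **Reactions change dosing.** A patient who would have exceeded 1.8 mg/m², but whose treatment was stopped or reduced after a reaction, is counted as absent with an ADR. This pulls the ratio below 1.
- **Longer treatment.** More cycles give more chances both to exceed the limit and to have an ADR, and a high-dose cycle after the reaction still makes the patient present. This pulls the ratio above 1. Number of cycles is not among the factors for these ADR tables, so they neither adjust for it nor show it.

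Protocol 7.2 and SAP 2.2 name myelosuppression, infection, hemorrhage and Grade 3 or higher events as outcomes whose background factors are to be investigated. This is the only per-cycle dose factor in those analyses. A ratio at or below 1 could be taken as reassurance about dosing above 1.8 mg/m², and a ratio above 1 as a dose signal. The table as planned supports neither.

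**Working it through.** **The plan's own figures.** The documents give no figure for this factor. The usual cycle total in Protocol 8.2 is 0.8 + 0.5 + 0.5 = 1.8 mg/m², so 'present' means above the usual total. The only design calculation concerns VOD/SOS: 88 per group, 18.5% against 6.2%, two-sided alpha 0.1. It reproduces at 80.2% with the rounded rates and at 80.4%, as stated, with 18.45% against 6.15%.

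**Assumptions (none from the documents).** ADR risk is the same at every dose, so the true ratio is 1. At most 6 cycles, with a 65% chance of a further cycle. Per-cycle ADR risk *h* is 10% or 30%. An uncut cycle exceeds 1.8 mg/m² with chance *q* = 5%, 15% or 30%, drawn either afresh each cycle or once per patient (a trait). A share *c* of ADRs cuts dosing (0, 50% or 100%), half of these by stopping treatment. The cut falls within the same cycle with chance *w* = 0 or 50%.

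**Hand check 1: cycle count alone** (fresh draws, *c* = 0, *q* = 0.15, *h* = 0.10).

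| Cycles k | 1 | 2 | 3 | 4 | 5 | 6 |
|---|---|---|---|---|---|---|
| P(k) | 0.3500 | 0.2275 | 0.1479 | 0.0961 | 0.0625 | 0.1160 |
| P(ever > 1.8) = 1 − 0.85^k | 0.1500 | 0.2775 | 0.3859 | 0.4780 | 0.5563 | 0.6229 |
| P(ADR) = 1 − 0.90^k | 0.1000 | 0.1900 | 0.2710 | 0.3439 | 0.4095 | 0.4686 |

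Weighting by P(k):

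- P(ever) = 0.3257, P(ADR) = 0.2313, P(both) = 0.0966.
- ADR risk if present = 0.0966/0.3257 = 0.297.
- ADR risk if absent = (0.2313 − 0.0966)/(1 − 0.3257) = 0.200.
- RR = 1.48 (simulated: 1.483).

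**Hand check 2: dose cuts alone** (trait, *c* = 0.5, *w* = 0.5, same *q* and *h*). A would-be exceeder is lost to 'absent' only if a Cycle 1 reaction cuts that cycle. The chance is m = h·c·w = 0.10 × 0.5 × 0.5 = 0.025.

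- Present: (0.2313 − 0.025)/(1 − 0.025) = 0.212.
- Absent: (0.85 × 0.2313 + 0.15 × 0.025)/(0.85 + 0.15 × 0.025) = 0.235.
- RR = 0.90 (simulated: 0.903).
- With m = 0, both risks are 0.2313 and RR = 1.00.

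**Simulation, 2,000,000 patients per scenario, no dose effect.**

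| Exceedance | ADRs that cut dosing | RR by the SAP's rule |
|---|---|---|
| Fresh each cycle | None | 1.27 to 1.64 |
| Fresh each cycle | Half (*w* = 50%) | 1.04 to 1.09 |
| Fresh each cycle | All (*w* = 50%) | 0.66 to 0.82 |
| Patient trait | Half or all (*w* = 50%) | 0.77 to 0.93 |
| Patient trait | None, or half but never in the same cycle | 1.00 |

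With exposure fixed before the outcome, the same data give 0.99 to 1.01, both for a landmark after Cycle 1 and for a time-dependent 'exceeded so far' rate ratio.

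**Other assumption sets.** With 20–40% exceedance per cycle drawn afresh, ADR risk of 15–40% in Cycle 1 and 10–15% later, and 1 to 6 cycles (30/35/20/10/3/2%), RR ran from 0.67 to 1.31. On the same inputs with exceedance as a trait it was 0.88 to 0.92 when half of reactions stop treatment and half cut the dose, 0.94 to 0.95 when 30% do each, and 1.00 to 1.01 with no cuts. With fresh draws and 15% doing each, it was 0.98 to 1.08. A further set gave 0.56 to 1.18, and 0.96 to 1.04 once exposure was fixed before onset.

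**The case against.** A reader might infer that the ratio must differ from 1, or that it must fall below 1 and so hide harm. The documents support neither. The two routes oppose each other, and some settings above return values at or close to 1. The lowest ratios need nearly every reaction to change dosing, while the action categories in SAP 8.2.3.1 include no action at all. The documents give no rate of exceeding 1.8 mg/m². Patients on the usual total are 'absent' anyway, so only would-be exceeders can be misplaced. Neither document itself draws a conclusion that higher dosing is harmless.

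The consequence is also bounded:

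- SAP 4.1 makes testing exploratory, and Protocol 8.14 concedes that confounding may not be adequately handled.
- The factor is absent from the VOD/SOS, liver-disorder and early-death lists, so the objective behind the 176 patients is untouched.
- At 176 patients and 20–40% exceedance per cycle, the 95% CI spans about a factor of 1.34 to 1.78 either side, generally wider than the bias in the moderate scenarios.
- At 5% trait exceedance about 9 patients (0.05 × 176 = 8.8) would be present, and SAP 8.2.3.4 lets the ratio be dropped for categories under 10.
- The SAP 9 listings allow the order of dose and reaction to be checked patient by patient.

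These points stand, and they limit the claim and its weight. They do not remove the fault: the ratio, CI and graph are still planned, and nothing in the SAP aligns exposure with onset. The SAP does respect sequence elsewhere: for VOD/SOS in 8.2.3.1, an onset before any transplant counts as absence of transplant.

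**Conclusion.** The point holds in conditional form. The SAP classifies exposure partly from cycles after the reaction and then takes a crude risk ratio. With no dose effect, that ratio can be biased below 1 or above 1, or can sit near 1. Across the assumption sets tried, the null ratio ran from roughly 0.6 to 1.6, with several settings near 1. That range describes the assumptions and does not predict the bias in this study, because the documents give no rates for exceeding the limit, for dose changes after reactions, or for cycles received. Aligning exposure with onset brought the null ratio back to about 1. Because the analysis is exploratory and the sized VOD/SOS question is unaffected, the change lies between worth considering and recommended; it is not essential.

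**What to change.** In SAP 5.4 and 8.2.3.4, use only dosing before first onset for myelosuppression, infection and hemorrhage (all grades and Grade 3 or higher) and for ADRs in at least 10% of patients, the threshold already used for onset timing in 8.2.3.1. Either of these would do:

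- A time-dependent 'exceeded 1.8 mg/m² so far' covariate in the Cox model of 8.1.4, censored at 28 days after the final dose.
- A landmark after Cycle 1: Cycle 1 dose against ADRs with onset after Cycle 1, in patients still on drug and free of that ADR.

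For rarer SOC/PT rows, give counts by this factor without a risk ratio or test, or footnote that exposure may follow the reaction. Cox models for every sparse PT are not practical.

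**Cost.** No new data: dosing dates, single doses, height and weight, and onset dates are already collected (Protocol 8.8.1, 8.8.3, 8.8.14). Early reactions would contribute little or nothing. On the Protocol 8.2 schedule the running total is 0.8 + 0.5 = 1.3 mg/m² by Day 8, so a modest excess crosses 1.8 only at the Day 15 dose. Precision is lower, the result may be a hazard ratio instead of a risk ratio, and confounding by patient condition remains.
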